CHAGNING HABITS AND LIFESTYLES IN OLDER INDIVIDUALS

Registration: NCT02777918

Date of Document: 26.07.2018

INCREASING EGG AND DIETARY PROTEIN INTAKE IN COMMUNITY-DWELLING OLDER ADULTS USING RECIPES AND SINGLE-USE HERB / SPICE PACKETS: A RANDOMIZED CONTROLLED TRIAL

METHODS

The study used a parallel group, randomized controlled intervention design, where community-dwelling older adults were randomized to receive or not receive high-protein egg-based recipes and herb/spice packets for 12 weeks, and egg intake, protein intake, and measures of health and well-being were measured at baseline, at the end of 12 weeks and after a further 12 weeks.

Participants

Older adults were considered for inclusion in the study if they were: 55 years and over; living in the community; not allergic to eggs; not knowingly suffering from hypercholesterolaemia or familial hypercholesterolaemia; not knowingly suffering from known renal insufficiency; not having undergone chemotherapy or radiotherapy in the last 6 months; not suffering from any condition, or receiving treatment that affected eating or sense of flavour; were able to give consent and complete all questionnaire measures; and did not have a pacemaker or defibrillator. These inclusion criteria allowed inclusion of volunteers within our target population (older adults living in the community), while ensuring against adverse health consequences as a result of a change in eggs or dietary protein consumption (British-Heart-Foundation, 2015; Pedrini, Levey, Lau, Chalmers, & Wang, 1996) or involvement in the study, and valid outcome assessments (Jacobsen et al., 1993; Steinbach et al., 2009; Van Cutsem & Arends, 2005).

Sample size:

Data from the National Diet and Nutrition Survey (NDNS) show that UK adults over 65 years old have a mean daily protein intake of 69.8g (SD = 20.3) (Bates et al., 2014). Assuming a threshold to stimulate muscle protein synthesis of 25-30g protein per meal (Paddon-Jones & Rasmussen, 2009) for three meals per day, daily intake should be at least 75-90g per day, an increase of on average 12.7g of protein per day. Assuming no change in the control group over the intervention period, and an alpha of 5% for a power of 0.8, the required sample size to detect a 12.7g increase in protein intake in the intervention group equals 41 participants per group. Taking into account a possible drop-out of 20%, we aimed to recruit 50 participants per study group.

Recruitment:

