Participants were recruited via contact lists of individuals who have volunteered in previous studies; organisations that ran group meetings within the target population, e.g. bridge clubs; and by flyers and posters at local community buildings, such as museums and libraries. All volunteers were initially screened for suitability by telephone or email, and they were sent a participant information sheet before coming to the University for the baseline test session. Screening was repeated at this test session, and consent completed. Participants were not informed of the aim of the study, but were instead told the project was studying habits and lifestyles in older adults.

Randomisation:

All eligible volunteers were randomized into one of two groups: intervention and control, following consent. Randomisation was stratified per ten year age group (55-64, 65-74, 75-85, 85+) and by earlier involvement in related research [ref], using blocks of 6-10 participants, with an exception that couples were always allocated to the same group. Randomization was undertaken by a researcher with no direct contact with participants ([name]).

Intervention

Community-dwelling older adults randomized to the intervention group received six high-protein egg-based recipes and herb/spice packets every two weeks to their home address, for twelve weeks. Recipes were intended to provide ideas for consuming eggs in different ways and using different flavours, to increase variety in the overall diet. Each recipe contained one or two eggs, and provided 25-30g of protein per meal.

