three questions: number of measures (eggs) per day, and the number of days per week they eat 'Boiled or poached eggs'; 'Fried eggs'; and 'Scrambled eggs or omelette'. Response options were used and converted to monthly egg intake as above.

Protein intake: Protein intake was measured using the complete SCG-FFQ, where food intake data were converted to protein intake and protein intake from animal sources, by the Scottish collaborative group (Clark, 2017). Protein intake from animal sources consisted of protein intake from meat, fish, eggs, and dairy foods. Protein intake is known to be related to egg intake (Ruxton, Derbyshire, & Gibson, 2010, questionnaire study), to muscle mass, strength and function (Houston et al., 2008; Loenneke, Loprinzi, Murphy, & Phillips, 2016; Tieland et al., 2012), and to positive health outcomes in older adults (Hannan et al., 2000; Lord, Chaput, Aubertin-Leheudre, Labonté, & Dionne, 2007). Animal based proteins contain all essential amino acids and are considered high quality protein sources (van Vliet, Burd, & van Loon, 2015). Animal protein stimulates a higher net protein synthesis than a high plant protein diet (Pannemans, Wagenmakers, Westerterp, Schaafsma, & Halliday, 1998). These measures also allowed investigation of any replacement of other high protein foods by egg based protein foods.

Adverse events: To assess adverse events, participants were asked whether during the previous month they had experienced any of the following effects more or less often than usual: nausea, digestive issues (e.g. constipation or diarrhoea), stomach aches/cramps, hunger, bloating/uncomfortable fullness, thirst, headaches, fatigue/tiredness, restlessness, dizziness, or skin rashes. If they answered yes to any of these questions, they were asked if they knew of any reason for this, or they had experienced anything else that was different than usual.

Secondary Outcomes:

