Functional measures of lean body mass: Physical performance was assessed using a short physical performance battery (SPPB) (Guralnik et al., 1994), consisting of three physical functioning tests measuring: lower body strength (chair stands), standing balance, and walking speed (8-foot walk). For the chair stands, participants were asked to stand up from a chair and sit down five times with their arms across the chest and time is measured. For the balance test, participants were instructed to stand in different positions: side-by-side, semi-tandem, and full-tandem position, while being timed for 10 seconds, or until they lost their balance. Walking was measured by asking the participant to walk an 8-foot walking course, at their usual speed, as if they were walking down the street to go to the shops. Times were recorded twice, and the fastest used for analyses. Scores from zero to four are derived for each of the three components and totalled following the instructions by Guralnik et al. (Guralnik et al., 1994). Total SPPB scores range from 0 to 12 with a higher score indicating better physical performance. The measures are relatively quick, include activities that are used in everyday life, and are non-invasive for the participants. SPPB measures have been linked to self-reported disability, predict mortality and nursing home admission (Guralnik et al., 1994), and have been recommended for measuring physical performance in frail old people (Cruz-Jentoft et al., 2010). Statistically significant improvements in SPPB scores have been found in older adults following increased protein intake (Tieland et al., 2012) and the method can measure clinically meaningful changes (Kwon et al., 2009).

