A schematic overview of the study design can be found in Figure 1. All participants came to Bournemouth University for a test session at baseline (T1), after 12 weeks intervention (T2), and after a further 12 weeks (T3). A week before each test session, participants received a set of questionnaires by post, to complete and bring to the test session. Queries were discussed at the test session, but on a few occasions, participants finished the questionnaires at home within a few days after the test session, and returned them by post. All test sessions were conducted in the morning between 8.00 and 11.00, at a time of the participant's preference. Participants came fasted, and were asked to have had only water to drink since going to sleep the night before the test session. Height and weight were measured first, followed by bioelectrical impedance measures of body composition. After these measures, a breakfast of toast / cereal and coffee / tea was provided. While the participant was eating breakfast, questionnaires were checked for missing values and any queries were discussed. After breakfast, the functional measures of lean muscle mass were undertaken. Questionnaires and tests undertaken were the same for each test session (T1, T2, T3), excepting that demographic and lifestyle characteristics, and reasons for eating / not eating eggs were only assessed at baseline. Test sessions were individual, or if preferred per couple, and lasted approximately an hour per person. After the baseline test session, all participants also received a postcard with a short dietary information message, including the importance of dietary protein for older adults and why it may be beneficial to eat more protein, and to do so for breakfast. This was included to add relevance to the recipes for those in the intervention group, but made no reference to the recipes or intervention, but was identical for all participants.

Blinding:

Outcome assessments were undertaken by a researcher who was blind to intervention group ([name]). Recipes and herb/spice packets were sent to intervention participants by a researcher with no direct contact with participants ([name]). Participants were not blind, although they were blind to the other possible conditions, thus the control group did not know about the intervention, nor the details of the intervention. Participants in the intervention group were asked not to mention the recipes to researchers.

Ethical Approval and Trial Registration

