Ethical approval for this study was granted by the Research Ethics Committee of Bournemouth University, prior to commencement. Participant recruitment started in May 2016, and test sessions were run from June 2016 to April 2017. The study was registered at ClinicalTrials.gov in May 2016 (NCT02777918).

Data analyses

Data were analysed using IBM SPSS Statistics for Windows, version 22, using an Intention-to-treat approach. First, all measures were tested for normality. All baseline measures were then compared

between the intervention and control group using χ^2 tests and Mann-Whitney U tests. Demographic and lifestyle characteristics were used to describe the sample. Correlations were investigated between all baseline measures. Multiple linear regression analyses were then used for the main analyses (Vickers & Altman, 2001). The effect of the intervention on all outcome measures was assessed using multiple linear regression, controlling for age, gender, baseline measures of the dependent variable, previous participation in related studies, and measures of total protein intake, BMI, usual physical activity and HR QoL score as assessed at the same time. Previous participation was included in regression models to allow for possible demand characteristics. Energy intake was not included in regression models following high correlations with BMI. Other demographic and lifestyle characteristics were also not included to maintain statistical power (Howell, 2012]. Separate regression models were used to predict egg intake, total protein intake, protein intake from animal sources, adverse events, lean body mass, physical performance, handgrip strength, and leg extensions as the dependent variables. Similar analyses were conducted once at the end of the 12 week intervention (T2) and once at the end of the following 12 weeks (T3). Egg intakes from the two different measures were compared using correlations and multiple linear regressions were conducted for both measures. Reasons for eating / not eating eggs and details on recipe feedback will be analysed further at a later date. These data and some of the data of participant demographic and lifestyle characteristics will be published elsewhere in exploratory analyses investigating intervention success / failure. Missing data were completed using last observation carried forward. Data are reported using means and standard deviations.

Figure 1: Schematic overview of the study design

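### The only effect model adjusts for total protein, BMI, activity and quality of life measured after randomisation, so it does not estimate the total intention-to-treat effect

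*Combined protocol and SAP*

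**What the plan says.** The Data analyses section declares an intention-to-treat approach and describes one multiple linear regression specification for the intervention effect on every outcome. It adjusts for age, gender, the baseline value of the outcome, previous participation in related studies, and "measures of total protein intake, BMI, usual physical activity and HR QoL score as assessed at the same time". The outcomes are listed without exception: "Separate regression models were used to predict egg intake, total protein intake, protein intake from animal sources, adverse events, lean body mass", and then physical performance, handgrip strength and leg extensions. The analysis is done once at T2 (12 weeks) and once at T3 (12 weeks later).

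The Procedure section shows that the four covariates exist at every visit: "Questionnaires and tests undertaken were the same for each test session (T1, T2, T3"). The exceptions it names are demographic and lifestyle characteristics and the reasons for eating or not eating eggs.

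Elsewhere total protein is what the intervention is meant to change. Under Sample size, "the required sample size to detect a 12.7g increase in protein intake in the intervention group equals 41 participants per group"; under Intervention, "Each recipe contained one or two eggs, and provided 25-30g of protein per meal". It is also the stated link to the muscle outcomes. The Protein intake paragraph relates it to muscle mass, strength and function, and under Functional measures of lean body mass we read: "Statistically significant improvements in SPPB scores have been found in older adults following increased protein intake".

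The section describes no unadjusted model, no model with baseline covariates only, and no sensitivity or mediation analysis.

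**The concern.** A covariate measured after randomisation can itself be changed by treatment. If it is, the group coefficient is no longer the total effect of being randomised to the intervention, which is what an intention-to-treat analysis should report. Total protein is the clearest case here, because the trial is designed to raise it.

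The consequences differ by outcome:

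- **Animal protein (primary).** It is a component of total protein: "Protein intake from animal sources consisted of protein intake from meat, fish, eggs, and dairy foods". Holding T2 total protein fixed changes the question from whether animal protein rose to whether it replaced other protein.
- **Lean mass and function (secondary).** Holding T2 protein fixed blocks part or all of the route by which the plan expects a benefit.
- **Total protein (primary).** No exception is written for its own model. Taken literally, the outcome is regressed on itself and the group coefficient is 0. It was presumably left out, and in that case no material bias is shown.
- **Egg intake and adverse events (primary).** Some loss is possible, through concurrent protein and concurrent HR QoL respectively, but the documents do not allow it to be sized.

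A real increase in animal protein, or a real gain in lean mass or function, could therefore be reported as small or null.

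**Working it through.** **1. The plan's own figure.** Inputs from Sample size: difference 12.7 g/day, SD 20.3 g, alpha 5% (two-sided assumed), power 0.8. Then n = 2 × (1.960 + 0.842)² × 20.3² / 12.7² = 40.1, so 41 per group. The figure reproduces. It rests on an unadjusted comparison of total protein, so the choice of covariates does not alter it.

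**2. Identity for animal protein.** Total = animal + other. Regressing T2 total protein on any set of covariates that contains T2 total protein gives a group coefficient of exactly 0. By linearity, the group coefficients for animal and other protein under the same covariates sum to 0. In one simulated data set of 100 people, with age, BMI, activity and HR QoL also in the model, they were +2.0623 and -2.0623. This needs no assumption about the data.

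**3. Size for animal protein.** The documents give no SD for animal protein and no T1–T2 correlation, so these are assumed. Notation:

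- sA, sO: SDs of animal and other protein, taken as uncorrelated and chosen so that sA² + sO² is close to 20.3². Splits: 18.5/8.4, 16.5/11.8 and 14.35/14.35.
- r: T1–T2 correlation of animal protein.
- dA: true rise in animal protein; D = 12.7: rise in total protein.

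With group, baseline animal protein and T2 total protein in the model:

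estimate = dA − b × D, where b = sA²(1 − r²) / [sA²(1 − r²) + sO²].

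Worked case (18.5/8.4, r = 0.6): b = 342.25 × 0.64 / (342.25 × 0.64 + 70.56) = 219.04 / 289.60 = 0.756. With dA = 12.7 the estimate is 12.7 × (1 − 0.756) = 3.1 g/day.

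All cases, g/day, splits in the order above:

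| r | dA = 12.7 (all of the rise is animal) | dA = 9.525 (75% is animal) |
|---|---|---|
| 0.4 | 2.50, 4.81, 6.90 | -0.67, 1.63, 3.73 |
| 0.6 | 3.09, 5.64, 7.74 | -0.08, 2.47, 4.57 |
| 0.8 | 4.62, 7.45, 9.34 | 1.45, 4.28, 6.16 |

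Simulation with 50 per arm (4,000 replicates) agrees within 0.1. With T1 instead of T2 total protein the estimates return to 12.7 and 9.5.

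**4. Power at r = 0.6, 50 per arm.** For dA = 9.525, the T1 model has 0.88, 0.94 and 0.98; the T2 model has 0.05, 0.26 and 0.66. For dA = 12.7, the T2 model still has 0.49, 0.83 and 0.98, so in that scenario the loss is mainly in the size of the estimate.

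**5. Check with a different parameterisation.** Take an animal protein SD of 12 to 18 g, a within-arm correlation of 0.7 to 0.9 between animal and total protein, and a rise that is all animal. Then estimate = 12.7 × (1 − correlation × SD / 20.3). This runs from 12.7 × (1 − 0.9 × 18/20.3) = 2.6 to 12.7 × (1 − 0.7 × 12/20.3) = 7.4 g/day, or 20% to 59% of the true effect.

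**6. Lean mass (illustration only).** Assume a 0.6 kg effect that runs wholly through protein. If lean mass follows the change in protein, with equal variances at T1 and T2, the within-arm slope of change on T2 level is 1 − r. The adjusted effect is then 0.6 × r: 0.24, 0.36 and 0.48 kg at r = 0.4, 0.6 and 0.8, where r is now the T1–T2 correlation of protein. Simulation gave 0.244, 0.359 and 0.471. If lean mass follows the T2 level of protein, the adjusted effect is about 0.

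**The case against.** The strongest objection is about timing. The covariate phrase follows closely on the baseline value of the outcome and previous participation. The only correlations described before the models are among baseline measures, and energy intake was dropped because of its correlation with BMI. The Outcomes section says some of the additional variables were used to control for confounding. All of this could suggest that baseline covariates were meant. However, only the dependent variable is labelled as baseline, and the models are defined at T2 and T3, so the concurrent reading remains the ordinary one. What stands is that the time point is not explicit. If T1 values were used, the model is sound and the sentence is wrong.

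Other points that stand in part:

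- The powered outcome, total protein, is not shown to be harmed if it was left out of its own model.
- Nothing in the documents says the intervention shifts BMI, activity or HR QoL. Adjusting for a concurrent variable that treatment does not affect generally adds no bias. The demonstrated problem is concurrent total protein.
- Every size above rests on assumed inputs, including zero correlation between animal and other protein. Letting that correlation run from -0.3 to 0.5 widens the 2.5–9.3 g/day range for a true 12.7 to 1.4–9.8. This is a modest change.
- The Protein intake paragraph does express interest in whether eggs replace other high-protein foods, and a fixed-total coefficient speaks to substitution. That supports it as an additional analysis, not as the only estimate of the intervention effect.

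**Conclusion.** The concern holds. As written, neither animal protein, one of the four primary outcomes, nor the lean mass and functional outcomes have a described model that estimates the total effect of randomisation. For animal protein the change of question is an algebraic fact once T2 total protein is in the model. Its size is illustrative: over the assumed splits and correlations of 0.4 to 0.8, a true 12.7 g/day is estimated as 2.5 to 9.3, and a true 9.5 as -0.7 to 6.2. For lean mass and function the loss is partial or complete, depending on how far the effect runs through protein and whether it follows protein change or level. No figure is claimed for egg intake or adverse events, and none for total protein if it was left out of its own model. The conclusion is conditional on the concurrent reading of the covariate sentence.

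**What to change.** First establish which time point was used for the four covariates.

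- **If T1 values were used:** correct the sentence to say that they were assessed at baseline (T1). Nothing else changes.
- **If T2 or T3 values were used:** make the primary model for every outcome group + baseline value of the outcome + age + gender + previous participation. If wanted, add total protein, BMI, activity and HR QoL as measured at T1, and amend the sentence to match. In the total protein model, enter baseline protein once, since it is already the baseline value of the outcome. Report the concurrent-covariate model only as a labelled exploratory analysis; for animal protein, describe it as a substitution analysis.

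The cost is small. All four covariates were measured at T1, so no data need collecting, and the 41 per group is unaffected. The T2 and T3 models must be re-run. Because the document is dated July 2018 and test sessions ended in April 2017, the change must be disclosed as post hoc.

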Our primary outcomes were egg intake, protein intake (total), protein intake from animal-based foods and adverse events. Secondary outcomes were lean body mass and various functional measures of lean body mass. Variables of potential influence on these outcomes were also assessed, to include various demographic and lifestyle characteristics, energy intake, BMI, usual physical activity levels, health-related quality of life, reasons for eating / not eating eggs, and recipe feedback (intervention group only) Morton et al., 2017). Some of these additional variables were included in analyses to control for potential confounding, some were used only to describe the sample and some were used to investigate further any reasons for intervention success or failure.

Primary Outcomes:

Egg intake: Egg intake was measured using two measures: an egg consumption Food Frequency Questionnaire (FFQ) measure [ref] and the egg section of a validated FFQ [SCG-FFQ, Clark, 2017; Masson et al., 2003]. The egg consumption FFQ requested frequency of consumption of 18 preparations of egg: boiled eggs (hot), hard boiled eggs (cold), fried eggs, scrambled eggs, poached eggs, omelettes, scotch eggs, quiches/savoury flans, egg sandwiches, egg salad, custards, meringues, sweet flan/crème caramel, duck/quail's eggs, raw eggs, egg yolk separate from the white, and egg white separate from the yolk. For each type of egg, participants were asked to complete number of measures (e.g. 1 egg, 1 slice) consumed per day (1, 2, 3, 4, 5+) on number of days per week, using response options 1 - 7 days per week, once or twice per month, or rarely / never. Responses were converted to number of eggs eaten per month, where the category 'rarely or never' was counted as 0 times eaten per month, 'once or twice per month' as 1.5 times, and 1 to 7 days per week, as 4, 8, 12, 16, 20, 24, and 28 times per month, respectively. All foods were considered to contribute equal portions of eggs, excepting the egg dishes custards, meringues, and sweet flan / crème caramel, where each consumption was considered as 0.5 portions, because a standard portion tends to be less than one egg.

The SCG-FFQ is a validated FFQ, developed by the Scottish collaborative group, measuring dietary intake over the last two-three months (Clark, 2017; Masson et al., 2003). The section on egg intake consists of

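### Adverse events, a primary outcome, are listed once for linear regression with no scoring rule, no handling of direction and no symptom-level analysis; if the 11 symptoms are pooled, a moderate rise in one would probably be missed

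*Combined protocol and SAP*

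**What the plan says.** The Outcomes section gives adverse events primary status: "Our primary outcomes were egg intake, protein intake (total), protein intake from animal-based foods and adverse events".

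Under Primary Outcomes, each participant reports, for the past month, whether "they had experienced any of the following effects more or less often than usual". The protocol then names 11 items for this question: "nausea, digestive issues (e.g. constipation or diarrhoea), stomach aches/cramps, hunger, bloating/uncomfortable fullness, thirst, headaches, fatigue/tiredness, restlessness, dizziness, or skin rashes". A yes prompts a question about the reason. Nothing is said about turning the answers into a score.

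The Data analyses section states: "The effect of the intervention on all outcome measures was assessed using multiple linear regression". It then lists the dependent variables: "Separate regression models were used to predict egg intake, total protein intake, protein intake from animal sources, adverse events", followed by the body-composition and functional measures. The models are run at T2 and again at T3. They adjust for age, gender, the baseline value, previous participation, and same-visit protein intake, BMI, physical activity and HR QoL. Results are given as means and standard deviations. No table or model by symptom is described.

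**The concern.** Three things are undefined for a primary safety outcome: how the 11 answers combine, what happens to less-often answers, and whether any single symptom is compared between arms.

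The natural reading is one pooled variable. Pooling adds the variability of unaffected items such as headache, thirst and restlessness to any change in the affected one. A mean and standard deviation of such a score cannot show which symptom moved. If worsening and improvement enter the same score, they may also offset each other. A pooled coefficient near zero would then say little about harm confined to one symptom.

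**Working it through.** **Inputs from the documents.** There are 11 symptoms (counted from the list), "an alpha of 5% for a power of 0.8", and a target of 50 per arm. The plan's own calculation is for protein: "detect a 12.7g increase in protein intake in the intervention group equals 41 participants per group". With the stated SD of 20.3 and a two-sided 5% level, n = 2 × (1.960 + 0.842)² × 20.3² / 12.7² = 2 × 7.849 × 412.09 / 161.29 = 40.1, rounded up to 41, so it reproduces. Inflating for drop-out gives 41 × 1.2 = 49.2, or 50. The documents give no symptom rates and no power for adverse events.

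**Assumptions.** Base rate per symptom 5, 10 or 20%; latent correlation between symptoms 0 to 0.5; every yes counted as harm; group comparison without covariates.

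**One symptom rises from 10% to 30%, symptoms independent, 50 per arm.**

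- *Count of 11.* The difference is 0.2. The variances are 11 × 0.09 = 0.99 (control) and 10 × 0.09 + 0.21 = 1.11 (intervention). SE = √[(0.99 + 1.11)/50] = 0.205, so z = 0.98. Power ≈ Φ(0.98 − 1.96) ≈ 16%.
- *Any-yes.* Control 1 − 0.9¹¹ = 0.686; intervention 1 − 0.9¹⁰ × 0.7 = 0.756; difference 0.070. The pooled SE is 0.0897 and the unpooled SE 0.0894. Power ≈ Φ[(0.070 − 1.96 × 0.0897)/0.0894] ≈ 12%.
- *The symptom alone.* Pooled SE = √(2 × 0.2 × 0.8/50) = 0.080; unpooled SE = √[(0.09 + 0.21)/50] = 0.0775. Power ≈ Φ[(0.2 − 1.96 × 0.080)/0.0775] = Φ(0.56) ≈ 71%. At 0.05/11 (critical value 2.84) it is about 36%.

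**Simulation, 20-point rise in one symptom, 50 per arm, 2,000 runs per row.**

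| Base rate | Correlation | Count | Any-yes | Symptom alone, 0.05 | Symptom alone, 0.05/11 |
|---|---|---|---|---|---|
| 5% | 0 | 25% | 24% | 86% | 54% |
| 5% | 0.3 | 17% | 20% | 87% | 53% |
| 10% | 0 | 16% | 12% | 74% | 38% |
| 10% | 0.3 | 9% | 11% | 75% | 38% |
| 20% | 0 | 11% | 5% | 58% | 25% |
| 20% | 0.3 | 7% | 7% | 59% | 25% |

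With correlation extended to 0.5, the ranges are about 6 to 25% pooled and 58 to 85% for the symptom alone. The differences of one or two points from the table are simulation error.

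**Other sizes of rise in one symptom (50 per arm, correlation 0 or 0.3).** At +10 points, pooled power is about 5 to 10% and the symptom alone about 20 to 40%. At +30 points the count has about 10 to 47%, and at +40 points about 15 to 70%.

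**All four digestive items rise together.** At 10% to 30% each, independent, the count difference is 4 × 0.2 = 0.8. The intervention variance is 7 × 0.09 + 4 × 0.21 = 1.47, SE = √[(0.99 + 1.47)/50] = 0.222, z = 3.61, and power ≈ Φ(1.65) ≈ 95%. Over the assumed base rates and correlations, the 11-item count has about 31 to 99% at +20 points each, and a four-item digestive count about 89 to 100%. At +10 points each (41 to 50 per arm, correlation 0 to 0.3) the figures are about 12 to 68% and 39 to 92%.

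**Direction.** Let m and l be the proportions answering more often and less often, with subscript 1 for intervention and 0 for control. A direction-blind yes compares (m₁ + l₁) with (m₀ + l₀). If m rises by δ while l falls by δ, the difference is zero. A net score summed over symptoms lets worsening in one item cancel relief in another. This was reasoned through, not simulated.

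**The case against.** **The single score is not stated.** Egg intake also appears once in the list, yet the section then says models were run for both of its measures. One label does not prove one model. This stands: pooling is an inference. It is a well-supported one, because the plan says where an outcome has two measures, and it describes totalling for the SPPB and SF-36. Adverse events has neither statement. If 11 linear models were intended, the plan should say so, and each would still be a linear model on a categorical answer.

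**Digestive upset would show in several items.** This also stands. A reader might infer that digestive harm would almost certainly be missed, or that the analysis has almost no power against the harms the list was meant to find. The documents do not support either reading. Four of the items overlap clinically, and a joint rise gives the pool moderate to high power in many scenarios. Even for one symptom, a large rise over a low base rate can be detected.

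**The comparison is uneven.** The 58 to 85% assumes the affected symptom is known and tested alone. Bonferroni over 11 lowers the figure at 10% to 30% to about 36%. Without correction, the chance of at least one false positive is 1 − 0.95¹¹ = 43% per time point if symptoms are independent. This is why the remedy should be estimates with intervals, not 11 tests.

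**The planned model has covariates.** Baseline adjustment could raise power. Adjusting for same-visit protein intake and HR QoL could absorb part of an effect. Neither was simulated, so the figures show the scale of dilution and not the exact power of the planned model.

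**Conclusion.** The point holds in a limited form. The adverse-events variable is undefined in scoring and direction, and no symptom-level analysis is planned for a primary outcome. On the pooled reading, a moderate rise confined to one symptom would probably be missed: about 6 to 25% power at +20 points, against about 58 to 85% for the symptom alone. These figures rest on 50 per arm, assumed base rates of 5 to 20%, latent correlation of 0 to 0.5 and an unadjusted 0.05.

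Pooling is not the only limit. At +10 points, even the single-symptom test is weak at this sample size. Nor do the documents say that a non-significant coefficient would be taken as absence of harm; that is only a risk if nothing else is reported. The change is worth making because symptom-level estimates would show which symptom moved, in which direction, and how imprecisely.

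**What to change.** In Data analyses, take adverse events out of the list of linear-regression outcomes. At T2 and at T3, for each of the 11 symptoms and for a digestive group (nausea, digestive issues, cramps, bloating), report:

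- n/N per arm, with more often and less often kept separate;
- the between-arm risk difference with a 95% confidence interval.

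If a pooled count is kept, define its scoring, including how direction is coded, and label it supportive.

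The data are already collected, so the cost is a change of wording and one extra table per time point. The downside is many intervals with no single p-value. They should be read as safety estimates and not as confirmatory tests, and an isolated finding should not be over-read.
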